7.2 Study Conduct

7.2.1 Accrual

For the Dose Evaluation Phase the analyses on accrual will be using the All Dose Evaluation Enrolled Subjects population. For the Dose Expansion Phase the analyses will be using the All 2-stage Enrolled Subjects population.

For each phase, the number of subjects enrolled and treated will be provided for the following:

- Enrollment summary by country and site.
- Enrollment summary by month.

A subject listing of accrual (informed consent date, first dose date, country, investigational site, and as treated dose level) will also be produced.

For the Dose Evaluation Phase, a distribution of the number of subjects by cohort will be provided for the DLT Period (number enrolled, treated and DLT-evaluable) and for the Dose Evaluation Phase itself (number enrolled and treated).

7.2.2 Relevant Protocol Deviations

For the Dose Evaluation Phase, the relevant protocol deviations will be summarized by cohort using the All Dose Evaluation Excluding DLT Treated Subjects population.

For the Dose Expansion Phase, the relevant protocol deviations will be summarized by cohort using the All 2-stage Treated Subjects population.

The following programmable deviations from inclusion and exclusion criteria will be considered as relevant protocol deviations. Non-programmable relevant eligibility and on-treatment protocol deviations, as well as significant (both programmable and non-programmable) eligibility and on-treatment protocol deviations will be reported through ClinSIGHT listings.

At Entrance:

- Subjects without histologically or cytologically-documented SCLC or without histologically-documented PAC.
- For PAC, subjects without current disease stage of IV.
- Subjects without measurable disease at baseline.
- Subject with baseline ECOG performance status > 1.
- For PAC, subjects without at least one prior line of chemotherapy for metastatic disease.
- For SCLC, subjects without at least one prior platinum therapy.
- Subject with prior therapy including any T cell co-stimulation or checkpoint pathways such as anti-PD-1, anti-PD-L1, anti-PD-L2, anti-CD137, or anti-CTLA-4 antibody, including ipilimumab and nivolumab; or other medicines specifically targeting T cells.

On-study:

- Subjects receiving concurrent anti-cancer therapy (chemotherapy, hormonal therapy, immunotherapy, non-palliative radiation therapy, standard or investigational agents for treatment of SCLC or PAC).

For each summary, a subject listing will also be produced.

7.3 Study Population

7.3.1 Subject Disposition

For the Dose Evaluation Phase, the enrolment will be summarized using the All Dose Evaluation Enrolled Subjects population.

For the Dose Expansion Phase, the enrolment will be summarized using the All 2-stage Enrolled Subjects population.

For each phase, the following enrolment summary will be provided (supporting listing will be supplied):

- Number of subjects enrolled, entering or not the treatment period,
- Reason for not entering the treatment period.

For the Dose Evaluation Phase, the discontinuation will be summarized by cohort using the All Dose Evaluation Treated Subjects population.

For the Dose Expansion Phase, the discontinuation will be summarized using the All 2-stage Treated Subjects population.

The following discontinuation summary will be provided (supporting listing will be supplied):

- Number of subjects who discontinued treatment,
- Reason for treatment discontinuation,
- Number of subjects who discontinued the study,
- Reason for study discontinuation.

For the tabulation of discontinuations during the Dose Evaluation Phase, if more than one cohort is to be reported pooled data across cohorts will also be presented.

7.3.2 Demographics and Other Baseline Characteristics

For the Dose Evaluation Phase, demographics and other baseline characteristics will be summarized by cohort using the All Dose Evaluation Treated Subjects population.

For the Dose Expansion Phase, demographics and other baseline characteristics will be summarized by cohort using the All 2-stage Treated Subjects population.

For the Dose Evaluation Phase, if more than one cohort is to be reported pooled data across cohorts will also be presented.

7.3.2.1 Demographics and Baseline Disease Characteristics

The following characteristics will be summarized. All baseline presentations will identify subjects with missing measurements. Demographic data will be listed.

- Age (in years, descriptive statistics),
- Age category (< 65, ≥ 65 and < 65, 65 - < 75, ≥ 75 years),

- Gender, Race, Ethnicity,
- Weight (kg),
- ECOG performance status (0, 1),
- Time from initial disease diagnosis to start of treatment (in years, descriptive statistics and by categories of: < 6 months, 6 months - < 1 year, 1 - < 2 years, 2 - < 3 years, ≥ 3 years),
- Disease stage at initial diagnosis (stage I, stage II, stage III, stage IIIA, stage IIIB, stage IIIC, stage IV),
- Cell type at initial diagnosis (adenocarcinoma, small cell carcinoma, other),
- For SCLC, disease classification at initial diagnosis (limited disease, extensive disease),
- Disease stage at current diagnosis (stage III, stage IV),
- Smoking status (current or former, never smoker, unknown),
- Alcohol Use (prior use, current use and, for each of these “none”, “average ≤ 2 drinks/day”, “average ≥ 3 drinks/day”),
- For PAC, family history of PAC (parent, grandparent, sibling),
- All lesions: presence of lesion, site of lesion, number of sites with at least one lesion (1, 2, 3, 4, ≥ 5),
- Target lesions: presence of target lesion, site of target lesion, number of sites with at least one target lesion (1, 2, 3, 4, ≥ 5), sum of reference diameters of target lesions (in mm, descriptive statistics and by categories of: < 20, 20 - 50, > 50 - 100, > 100).

7.3.2.2 Prior Cancer Therapy

Agents and medication will be reported using the generic name. The following prior cancer therapy will be summarized:

- Line of therapy (first, second, third, other - note: the intent is for a line of therapy for metastatic disease. Adjuvant therapy for PAC subjects should not be considered to define line of therapy),
- Best response to most recent prior systemic therapy regimen (CR or PR, SD, PD, unknown or not reported),
- Primary reason regimen was discontinued (disease progression, maximum clinical benefit, toxicity, completed treatment, other),
- Time from completion of most recent prior systemic therapy regimen to start of treatment (< 1, 1 - <3, 3 - 6, > 6 months),
- For SCLC, prior medication response on platinum based therapy (resistant/refractory, sensitive, unknown or not reported),
- Prior surgery related to cancer (yes or no),
- Prior radiotherapy (yes or no),
- Prior systemic cancer therapy classified by therapeutic class and generic name.

7.3.2.3 Other Baseline Medical Evaluations

General medical history and pretreatment events will be tabulated. Prior/current non-study medication classified by anatomic class, therapeutic class and generic name will be tabulated and listed.

7.3.3 Baseline Laboratory Examinations

Baseline laboratory data needed for the CSR will be extracted from the on-treatment shift tables in toxicity grading from baseline (see [Section 7.6.12.1](#)).

7.4 Extent of Exposure

For the Dose Evaluation Phase, extent of exposure will be summarized by cohort using the All Dose Evaluation Treated Subjects population.

For the Dose Expansion Phase, extent of exposure will be summarized by cohort using the All 2-stage Treated Subjects population.

Extent of exposure will be presented separately for ulocuplumab and for nivolumab. A listing of study medication dosing (infusion details and dose modification) and a listing of batch number will also be provided.

7.4.1 Study Therapy

Below table summarizes the key parameters that will be used to calculate dosing data.

Table 7.4.1-1: Administration of Study Therapy: Definition of Parameters

	Ulocuplumab	Nivolumab
Assigned Starting Dose	DL-1: 200mg weekly DL1: 400mg weekly DL2: 800mg weekly DL3A: 1600mg weekly	3mg/kg every 2 weeks
Dose	Dose (mg) is defined as total dose administered at each dosing date	Dose (mg/kg) is defined as total dose administered at each dosing date (mg) divided by the most recent weight (kg). Dose administered and weight are collected from the CRF
Cumulative Dose	Cumulative dose (mg) is the sum of the doses administered to a subject during the treatment period	Cumulative dose (mg/kg) is the sum of the doses administered to a subject during the treatment period
Relative Dose Intensity (%)	Cumulative dose divided by [(Last dose date - Start dose date + 7) × assigned starting dose in mg / 7] × 100	Cumulative dose divided by [(Last dose date - Start dose date + 14) × 3 / 14] × 100
Duration of Treatment (days)	Last dose date - Start dose date + 1	Last dose date - Start dose date + 1

The following parameters will be summarized:

- Number of doses received (descriptive statistics),
- Cumulative dose (descriptive statistics),
- Relative dose intensity ($\geq 110\%$, $90 - < 110\%$, $70 - < 90\%$, $50 - < 70\%$, $< 50\%$),
- Duration of study therapy (months) using:
 - A Kaplan-Meier curve whereby the last dose date will be the event date for those subjects who are off treatment. Subjects who are still on-treatment will be censored on their last dose date.
 - Descriptive statistics (minimum, maximum, KM median with 95% CI and by categories of: > 3 months, > 6 months, > 9 months, > 12 months as well as number off treatment).

7.4.2 Modifications of Study Therapy

7.4.2.1 Infusion Interruption and Infusion with IV Rate Reduction

Each ulocuplumab or nivolumab infusion can be interrupted and/or the IV infusion rate can be reduced. The following parameters will be summarized using CRF data:

- Number of subjects with at least one infusion interrupted,
- Number of infusion interrupted per subject (0, 1, 2, 3, ≥ 4),
- Total number of infusions interrupted / total number of infusions received,
- Reason for infusion interrupted (any).

Similar summaries will be provided for infusion with IV rate reduction.

7.4.2.2 Dose Delay

Derived data will be used for reporting dose delay. Starting from the second dose, a dose will be considered as actually delayed if the delay is exceeding 3 days (i.e., greater than or equal to 4 days from scheduled dosing date) for nivolumab or 2 days (i.e., greater than or equal to 3 days from scheduled dosing date) for ulocuplumab. It is defined as “duration since previous administration in days -7” for ulocuplumab or as “duration since previous administration in days -14” for nivolumab. The following parameters will be summarized:

- Number of subjects with at least one dose delayed,
- Number of dose delayed per subject (0, 1, 2, 3, ≥ 4),
- Total number of doses delayed / total number of doses received,
- Reason for dose delayed,
- Length of delay (4 - 7 days, 8 - 14 days, 15 - 42 days, > 42 days; for ulocuplumab, the first class is 3 - 7 days).

The reason for dose delayed will be any reasons supplied by the investigator for the period during which a dose delay was determined. If the reason corresponding to the dose delay (as defined by above algorithm) is missing then 'Not reported' will be provided.

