### **3.1.4 Dose Limiting Toxicity**

The incidence of DLT(s) assessed in the first 3-6 evaluable subjects per tumor type (if applicable) during the first 6 weeks will be used to initially determine whether a dose level is tolerable. A subject will be considered evaluable for DLT if they have received at least 5 out of 6 ulocuplumab doses and at least 2 out of 3 nivolumab doses in a 6 week dosing period or experienced a DLT. DLT should not be AE considered by the investigator to be disease related. The following drug-related AE (whether related to one or both agents) will be considered a DLT:

- Any Grade  $\geq 3$  drug-related non-hematological AE, including the following laboratory abnormalities
  - If a subject has baseline Grade  $\leq 1$  AST, ALT, or total bilirubin, a drug-related Grade  $\geq 3$  toxicity will be considered a DLT
  - If a subject has baseline Grade 2 AST or ALT, drug-related elevations in AST and/or ALT  $> 2x$  baseline or a maximum of  $> 8x$  ULN will be considered a DLT
- Any Grade 4 drug-related hematological AE or hematological or non-hematological laboratory abnormality with the following exceptions:
  - Grade 4 amylase or lipase not associated with symptoms or clinical manifestations
  - Grade 4 lymphocytopenia not associated with symptoms or clinical manifestations
- Any drug-related AE that results in dose reduction of ulocuplumab during the DLT period
- Any drug related AE that results in dose delay of ulocuplumab  $> 14$  days during DLT period
- Any toxicity managed by discontinuation of ulocuplumab (see [section 4.5.3.1](#))
- Any toxicity managed by discontinuation of nivolumab (see [section 4.5.3.2](#))

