##### **4.5.1 Dose Delays and Interruptions**

###### **4.5.1.1 Ulocuplumab Dose Delay**

Investigators should, whenever possible, determine which medication is causing the toxicity and delay or dose reduce ulocuplumab and/or delay nivolumab, as applicable. If ulocuplumab is delayed due to an AE, nivolumab dosing may continue at the discretion of the Investigator. Ulocuplumab should be delayed for the following:

- Any Grade  $\geq 3$  drug-related AE, including laboratory abnormalities except for Grade 3 AEs that do not require nivolumab dose delay (see [section 4.5.1.2](#))

If the decision is to resume ulocuplumab dosing, the subject should restart treatment on the next regularly scheduled ulocuplumab dosing visit. Skipped doses are not to be replaced. If treatment is delayed > 6 weeks, the subject must be permanently discontinued from ulocuplumab therapy.

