**4.5.3 Discontinuation Criteria**

**4.5.3.1 Ulocuplumab Discontinuation Criteria**

Discontinuation criteria apply for all drug-related AE attributed to ulocuplumab and consist of the following:

- Grade ≥ 3 thrombocytopenia associated with bleeding (occurring concomitant with ≥ Grade 2 hemorrhage)

- Grade  $\geq 3$  drug-related infusion reaction of any duration
- Any Grade 4 drug-related AE or laboratory abnormality except for Grade 4 AE listed as exceptions to the nivolumab discontinuation criteria (see section 4.5.3.2)
- Any recurring drug-related Grade  $\geq 3$  AE or laboratory abnormality that requires multiple dose reductions of ulocuplumab (see specific criteria in [section 4.5.2.1](#))
- Any drug-related AE resulting in dose delay of ulocuplumab  $> 6$  weeks
- Any AE, laboratory abnormality, or intercurrent illness which, in the judgment of the Investigator, presents a substantial clinical risk to the subject with continued ulocuplumab dosing

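### A dose hold that is never followed by another dose adds nothing to the SAP's dose-delay summary and does not lower relative dose intensity

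*SAP*

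**What the plan says.** **Delay.** SAP 7.4.2.2 derives delays from dosing dates: "Starting from the second dose, a dose will be considered as actually delayed if the delay is exceeding 3 days" for nivolumab, and 2 days for ulocuplumab. The length is "duration since previous administration in days -7" for ulocuplumab and "duration since previous administration in days -14" for nivolumab. The rate shown is "Total number of doses delayed / total number of doses received". Length classes run up to a class of more than 42 days.

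**Dose intensity.** In SAP Table 7.4.1-1 the ulocuplumab RDI denominator spans "Last dose date - Start dose date + 7" days; for nivolumab the added term is 14. Neither section has a rule for a hold that no dose follows.

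**Protocol.** A dose delay here is the hold itself and needs no later dose.
- Section 3.1.4 makes a DLT of "Any drug related AE that results in dose delay of ulocuplumab" for more than 14 days in the DLT period.
- Section 4.5.1.1 says that after more than 6 weeks "the subject must be permanently discontinued from ulocuplumab therapy".
- Section 4.5.3.1 lists "Any drug-related AE resulting in dose delay of ulocuplumab" beyond 6 weeks as a discontinuation criterion.
- Section 4.5.1.2 applies a 6-week limit to all study therapy, subject to the exceptions in 4.5.3.2.

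**The concern.** Holds with no later dose are an expected outcome under this protocol. The 6-week rules create them. So does the DL-1 column of protocol Table 4.5.2.1-1, where the main Grade 3 or higher row has ulocuplumab held and then discontinued at the first event. SAP section 2 states that DL-1 has been opened after more than 2 DLTs at DL1.

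The dose-delay and RDI tables are therefore likely to be read as evidence on tolerability, and SAP 7.5.1 lets the recommended dose rest on all available safety and efficacy data. On these two measures, a subject who recovers and resumes looks worse than one with the same hold who never resumes. The delay summary is biased downward, most of all for long holds.

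**Working it through.** The documents give no RDI or delay figure to reproduce. I applied the SAP's formulas to illustrative dosing histories, which are assumptions.

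**Formulas (SAP 7.4.1 and 7.4.2.2)**
- Ulocuplumab RDI = cumulative mg ÷ [(last − first + 7) × assigned mg ÷ 7] × 100. Delay = gap − 7.
- Nivolumab RDI = cumulative mg/kg ÷ [(last − first + 14) × 3 ÷ 14] × 100. Delay = gap − 14.

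Check: ulocuplumab 200 mg on Days 1, 8 and 15 gives 600 ÷ [(15 − 1 + 7) × 200 ÷ 7] = 600/600 = 100% and no delay, as it should. With full doses the mg amount cancels, so the results hold at any dose level.

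**Same hold, with and without a later dose**

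| History | SAP delay | SAP RDI | Given / due through resumption day |
|---|---|---|---|
| Ulocuplumab Days 1, 8; resumes Day 57 | 57 − 8 − 7 = 42 days | 600 ÷ (63 × 200/7) = 600/1800 = 33% | 3/9 = 33% |
| Ulocuplumab Days 1, 8; never resumes | none | 400 ÷ (14 × 200/7) = 400/400 = 100% | 2/9 = 22% |
| Nivolumab Days 1, 15; resumes Day 71 | 71 − 15 − 14 = 42 days | 9 ÷ (84 × 3/14) = 9/18 = 50% | 3/6 = 50% |
| Nivolumab Days 1, 15; never resumes | none | 6 ÷ (28 × 3/14) = 6/6 = 100% | 2/6 = 33% |

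A delay of exactly 42 days is not over 6 weeks, so resumption falls within the limit. At DL-1 it could arise, for example, where ulocuplumab was held only because nivolumab was (protocol 4.5.1.2). In the SAP's rate, the two ulocuplumab subjects together show 1 delayed dose out of 3 + 2 = 5 received, although both were held.

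**Other histories.** With 1, 2, 3 or 6 full on-time doses of either drug and a final hold of 14, 28, 42 or 49 days, RDI is 100% with no delays in every case. If dosing resumes after three ulocuplumab doses, a 28-day hold gives RDI 50% and a 42-day hold gives 40%, each with one delay.

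**Where earlier doses were late.** Ulocuplumab on Days 1, 8, 22, 29 and then a final hold: 800 ÷ (35 × 200/7) = 80%, with one 7-day delay (22 − 8 − 7). Days 1, 8, 29 and then a final hold: 600/1000 = 60%, with one 14-day delay (29 − 8 − 7). RDI keeps its value at the last dose; the final hold adds nothing.

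**The class above 42 days.** For ulocuplumab, protocol 4.5.1.1 rules out resumption after such a delay without qualification. What can remain is protocol deviations, a day of visit window, or a delay allowed under the 4.5.3.2 exceptions if they extend to ulocuplumab.

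**An undefined term.** Exposure is presented by drug (SAP 7.4), so I took the last dose date as drug-specific. Table 7.4.1-1 does not say so. If it meant the last dose of either drug, three weekly ulocuplumab doses with nivolumab continuing to Day 57 would give 600/1800 = 33%, not 100%.

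**The case against.** RDI to the last dose is a legitimate measure of delivery while a subject is being dosed, and treatment duration captures stopping. SAP 7.4.1 also reports number of doses, cumulative dose and Kaplan-Meier duration. In the ulocuplumab example the discontinued subject has 2 doses, 400 mg and 8 days; the one who resumed has 3 doses, 600 mg and at least 57 days. So a reader should not infer that the exposure section as a whole favours the subject who tolerated treatment worse. That objection stands, and it is why the existing parameters should be kept.

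Nor is the event hidden. Discontinuations and reasons appear in SAP 7.3.1 and 7.4.2.3, and AEs leading to discontinuation in 7.6.4. The dosing listing in 7.4 is also available, and AEs leading to dose delay are in 7.6.5. It is tempting to say that 7.6.5 will contradict the delay table. That cannot be shown, because 7.6.5 does not state whether it uses the CRF action taken or the derived delay. What remains is that none of these summaries gives the length of a final hold or the dose lost.

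Finally, one might call the ulocuplumab class above 42 days empty by construction. Protocol 4.5.1.2 ties ulocuplumab delay to nivolumab delay and carves the 4.5.3.2 exceptions out of a rule about all study therapy, while 4.5.1.1 has no exception. The protocol is unclear on this, so the class is nearly empty at most.

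**Conclusion.** The point holds for the derived dose-delay summary and for RDI. A hold with no later dose of that drug adds no delay and does not reduce RDI, whereas one further dose changes both: 33% against 100% in the ulocuplumab example, 50% against 100% for nivolumab. A reader might infer that every such subject is reported at 100%; that is true only if all earlier doses were full and on time.

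The consequence is confined to descriptive exposure and tolerability summaries. ORR, the Simon thresholds and the DLT counts do not use these derivations. The size across the trial is unknown, because the documents give no frequency of such holds. The result assumes a drug-specific last dose date and that the Data Presentation Plan, which was not available, adds no rule for them.

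**What to change.** Keep the current parameters and add to them.

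1. In SAP 7.4.2.2, add a separate line for holds that ended in discontinuation or were ongoing at cut-off. Limit it to scheduled doses withheld before the decision to discontinue that drug, so that stops for progression or withdrawal are not counted. Report the reason, and the length from the scheduled date to that drug's discontinuation decision or the data cut.
2. In Table 7.4.1-1, add a supplementary RDI whose denominator is the doses due up to that same date. Say whether a dose due on the date itself counts: in the ulocuplumab example it decides between 2/9 = 22% and 2/8 = 25%.
3. State that the last dose date is drug-specific.
4. Reconcile protocol 4.5.1.1 and 4.5.1.2 on whether the 4.5.3.2 exceptions reach ulocuplumab.

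The cost is SAP wording, minor programming and a short protocol clarification. The sponsor must confirm that the CRF holds a discontinuation date for each drug: protocol Table 5.1-5 relies on a date of discontinuation but does not say it is drug-specific. Reported delays and dose intensity will look less favourable.

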7.4.2.3 Ulocuplumab Partial Dose Discontinuation

Ulocuplumab can be discontinued while the subject is continuing on nivolumab alone. The following parameters will be summarized using CRF data:

- Number of subjects with ulocuplumab discontinuation,
- Reason for ulocuplumab discontinuation.

7.4.3 Concomitant Medications

Concomitant medications are medications other than study medications which are taken at any time on-treatment (i.e. on or after the first day of study therapy and within 100 days following the last dose of study therapy). Concomitant medication classified by anatomic class, therapeutic class and generic name will be tabulated and listed.

7.4.4 Immune Modulating Medications

Concomitant IMM classified by anatomic class, therapeutic class and generic name will be tabulated as a whole and separately for the following use:

- AE management,
- Immunomodulating treatment for AE,
- Infusion-related
- Premedication,
- Other use.

Concomitant IMM will be listed.

